### 5.3.1 Assessment of violation of inclusion and exclusion criteria ex post

The violation of inclusion and exclusion criteria ex post does not generally result in excluding a patient from the study. In case that a randomized patient did not meet inclusion/exclusion criteria at the time of recruitment, the ZKS data management has to be informed as soon as possible. The principal investigator ([name]. [name]) will decide about how to proceed with the patient in consultation with the project management (ZKS Leipzig). In any case, the documentation of the patient will be continued.

## 5.4 Description of the study procedure

Following the baseline visit including randomization (see 5.3), patients will receive active treatment or control (fNIRS neurofeedback/EEG neurofeedback) or delayed treatment which involves a period of 8 weeks without treatment. If a patient was randomized into the delayed treatment condition, the following variables will be assessed prior to the treatment 8 weeks after randomization:

Time point	Variable
Only delayed treatment  Before start of therapy Week 8 (+ max. 2 weeks)	
 
Anamnesis
 
Comorbidities
 
Medication intake
 
Anthropometry
 
Sociodemographics
 
Eating disorder psychopathology e.g., Eating Disorder Examination (EDE)
 
General psychopathology e.g., Patient Health Questionnaire (PHQ)
 
Neuropsychological and brain activity-related measures e.g., Go/NoGo task
 
Behavioral measures e.g., Bogus taste test
 
Visual analogue scales (VAS): expectations, motivation
 

During treatment, all patients will be assessed weekly (i.e. at each treatment session), including the following variables:

Time point	Variable
During treatment, weekly Active treatments: Weeks 1-7 Delayed treatment: Weeks 9-15	
 
Brain activity-related outcomes e.g., EEG frequency band power
 
Visual analogue scales (VAS): state craving, liking, sense of control, hunger, satiety, and mood
 
Objective binge-eating episodes
 
(Serious) adverse events
 

The following variables will be assessed at the end of treatment, 8 (fNIRS neurofeedback and active control treatments) or 16 (delayed treatment control condition) weeks after randomization.

Time point	Variable
End of therapy (t1) Active treatments: Week 8 (max. + 2 weeks) Inactive control: Week 16 (max. + 2 weeks)	
 
Comorbidities
 
Medication intake
 
Randomization
 
Anthropometry
 
Sociodemographics
 
Eating disorder psychopathology e.g., Eating Disorder Examination (EDE)
 
General psychopathology e.g., Patient Health Questionnaire (PHQ)
 
Executive functions e.g., Behavior Rating Inventory of Executive Functions (BRIEF-A)
 
Neuropsychological and brain activity-related measures e.g., Go/NoGo task
 
Behavioral measures e.g., Bogus taste test
 
Visual analogue scales (VAS): expectations, motivation, and treatment evaluation
 

## 5.5 Follow-up

Six months after the end of treatment, all patients will be followed-up assessing the following variables:

Time point	Variable
Follow-up (t2) Month 6 (max. + 2 weeks)	
 
Comorbidities
 
Medication intake
 
Anthropometry
 
Sociodemographics
 
Eating disorder psychopathology
 

	
e.g., Eating Disorder Examination (EDE)
 
 
• General psychopathology e.g., Patient Health Questionnaire (PHQ)
 
• Executive functions e.g., Behavior Rating Inventory of Executive Functions (BRIEF-A)
 
• Behavioral measures e.g., Bogus taste test
 

--	---------------------------------------------------------------------------------------------------------------------------------------------------------------------------------------------------------------------------------------------------------------------------------------------------------------------------------------

## 5.6 Premature drop-out from treatment or follow-up

Every drop-out from treatment and/or follow-up will be documented by the study team and sent to the ZKS data center, including the exact date of withdrawal as well as the circumstances and reasons for withdrawal, as far as possible.

### 5.6.1 Discontinuation of the study intervention for individual patients

A patient may withdraw from the study at any time, at his or her own request, for any reason, specified or unspecified, and without penalty or loss of benefits to which the patient is otherwise entitled. Patients who have withdrawn from the study will not be allowed to re-enter later.

Furthermore, the responsible investigator has the right to discontinue the treatment of patients that experience one or more of the following incidents:

1. Adverse events (AE) or serious adverse events (SAE), particularly serious medical or psychological problems (e.g., cardiovascular disease, suicidal tendency, major depression) which do not allow any further treatment with the investigational intervention or which do not allow any further participation in the study because of impaired interpretability of the study results;
2. Reasons precluding attendance of scheduled visits;
3. Unacceptable benefit/risk ratio;
4. Lacking cooperation or compliance of the patient (i.e., intake of medication that is prohibited by the study protocol, intake of psychotropic or weight-affecting medications without indication, participation in psychotherapeutic interventions other than the study);
5. Refusal of the patient to continue participation.

The responsible investigator will make the decision about discontinuing treatment after contacting the coordinating investigator. Date of discontinuation, all recorded results at that time and, if known, the reasons for discontinuation are to be documented in the case report forms (CRFs). If possible, a final examination will be done. In any case, all patients will be followed up at each assessment time point after discontinuation, according to the intention-to-treat principle.

## 6 ADVERSE EVENTS (AE/SAE)

### 6.1 Adverse events and serious adverse events (AE/SAE)

#### 6.1.1 Definition

The Declaration of Helsinki and the ICH-GCP Guideline E6 (point 4.11 and 5.17) set the protection of

participants in clinical trials in the first place. Therefore, the safety and harmlessness of interventions and therapies without drugs have to be proved in clinical trials.

The DIN EN ISO 14155:2011, section 3.2 defines adverse events (AE) as follows:

**Adverse Events (AE) are**

all in subjects, user or other persons occurring adverse medical events, unintended disease or injuries or undesirable clinical diagnoses (including abnormal laboratory results), regardless of whether these are related to the investigational product or not.

NOTE 1: Includes events associated with the test product or the comparison product.

NOTE 2: Includes events related to the procedure in question.

NOTE 3: For users or others persons the definition is limited to events associated with the test product.

Serious adverse events (SAEs) are according to § 2 No. 5 MPSV defined as follows:

**"Serious adverse event** is any problem encountered in a licensable clinical trial or a licensable performance evaluation unwanted event that has led directly or indirectly to death or to a serious deterioration in the health of a subject or user or any other person, could have led or could lead without regard to whether the event was caused by medical device; what has been stated applies to serious adverse events, which was issued in a clinical trial or performance evaluation for which an exemption from the permit requirement in § 20 paragraph 1 sentence 2 of the Medical Devices Act, have occurred."

DIN EN ISO 14155:2011, section 3.37 defines serious adverse events as follows and specifies what serious deterioration of the health status are:

An Adverse Event is defined to be serious if it:

**a. resulted in death,**

**b. resulted in a serious impairment of health of the subject, either**

- results in a life-threatening illness or injury, or
- results in a permanent disability of body structure or function, or
- requires in-patient hospitalization or prolongation of existing hospitalization, or
- results in a medical or surgical procedure in order to prevent a life-threatening illness or injury or a permanent injury to a body structure or function

**c. is a congenital abnormality/birth defect.**

NOTE: A scheduled hospitalization due to pre-existing conditions or requested by the CIP process, without a significant worsening in health is not considered a serious adverse event.

### 6.1.2 Documentation of adverse events (AE)

AEs will be documented at the AE form including the following information: start, end, description, date, intensity, causality, and consequence. The documentation of AEs will be realized for all intervention arms including the delayed treatment group during the study (from study inclusion to last follow-up visit).

Inpatient treatment of comorbidities, for example, a massive worsening of psychiatric symptoms, must be classified as SAEs and documented in the AE form.

### 6.1.3 Documentation of serious adverse events (SAE)

SAEs will be documented in the AE form, which contains additional questions for SAEs. At first, the original form remains at the study center. After the end of treatment (week 8 or 16, respectively) and

follow-up visit (month 6), the original AE form will be sent to the ZKS data management or handed to the monitoring staff together with all other case report forms. If additional information to the SAE are available at a later time point, they will be documented as well and sent to the ZKS data management or monitoring staff, respectively. SAEs will be documented during the patient's study period (from study inclusion to last follow-up visit). SAE involving patient's death will be immediately reported to the principal investigator. The study team will provide additional required information upon request. Confidentiality of patients' data will be protected by a documentation system working with anonymous patient codes. The primary notification as well as all following notifications of SAEs must be assignable to each other via the patient's identification number.

## **6.2 Device deficiency (DD)**

### **6.2.1 Definition**

Documentation and reporting of product deficiency, including serious product defects and events, is carried out as in clinical routine in accordance with the requirements of the MPSV §3. NeuroConn GmbH, Ilmenau, Germany (EEG) is thus responsible for examining occurred product defects and possibly related messages. Investigators and producers are responsible for reporting incidents to the competent authority.

Meets a defect the definition of SAEs, the documentation and reporting requirements described in section 6.1 should be considered.

## **6.3 Safety analyses**

Every patient will be monitored closely regarding safety during the course of the study and includes the assessment of AEs and SAEs at the end of treatment (t1) and follow-up (t2). All AEs and SAEs will be analyzed descriptively in the final analysis.

## **6.4 Comorbidities**

If an extreme worsening of the patient's mental health is noticed by the study therapist during neurofeedback sessions, short-term inpatient treatment should be considered. If admission to inpatient treatment is not considered necessary, two outpatient appointments outside the study schedule are allowed for crisis intervention. Neither inpatient nor outpatient treatment may be conducted by the study therapists. Inpatient treatment due to psychiatric reasons lasting more than one week will result in treatment drop-out/study discontinuation. Similarly, if the patient received two appointments for crisis intervention, the patient will be classified as treatment drop-out/non-completer (see paragraph 5.6.1).

## **6.5 Therapeutic actions**

When the patient is in need for treatment due to an adverse event, the treatment/intervention must be applied according to current standards of medical research to rehabilitate patient's health. In medical emergency, appropriate equipment and medical products for reanimation have to be available, in order to treat the patient as quick as possible.

The treatment of AEs and SAEs must be documented.

In general	Regarding intervention
The initiated intervention must be documented at the respective place in the CRF and/or using additional records.	
 
• Treatment interrupted
 
• Treatment modified
 
• Treatment not interrupted
 
• Unknown
 
• Not applicable
 

## 7 BIOMETRIC ASPECTS OF THE STUDY

### 7.1 Randomization algorithm

Randomization will be performed using an online tool programmed by the ZKS Leipzig (IFB Data centre).

The arm balance will be 1:1:1 and will be stratified by

- BMI (< 35.0 kg/m^2 vs. ≥ 35.0 kg/m^2)
- sex
- behavioral weight loss treatment status

A minimization algorithm based on Pocock and Simon will be used.

### 7.2 Endpoints

#### 7.2.1 Primary endpoint

The number of objective binge-eating episodes (OBEs) over the past 14 days at post-treatment (t1), derived from the well-established Eating Disorder Examination interview, **will be compared between groups, correcting for the baseline value**. OBEs are consistently reported as the primary outcome measure in BED treatment trials.

#### 7.2.2 Secondary endpoints

- (a) Feasibility (between t0-t1): Recruitment, attrition, assessment completion, compliance, patients' program evaluation
- (b) Number of OBEs (t0, t2), remission from objective binge eating (EDE) (t0-t2), eating disorder psychopathology (EDE-Q) (t0-t2)
- (c) Neuropsychological and neurophysiological outcomes (t0, t1): e.g., inhibition (Go/NoGo task)
- (d) Weight management-related behaviors (t0-t2): e.g., self-efficacy (GSES)
- (e) Mental health (t0-t2): e.g., depressive symptoms (PHQ-D)
- (f) Physical health (t0-t2): e.g., body mass index (kg/m^2)

### 7.3 Statistical description of the trial hypothesis

This clinical trial evaluates whether neurofeedback results in fewer objective binge-eating episodes after

end of treatment (i.e., 2 months after randomization) than a delayed treatment group. Furthermore fNIRS neurofeedback, EEG neurofeedback, and delayed treatment will be compared.

## 7.4 Sample size

### 7.4.1 Estimates of effects

Two clinical trials by the same group analyzed the effects of EEG neurofeedback on binge eating and found effect sizes of 0.64 and 0.65. Preliminary data for BED showed an effect size within a treatment group of 0.40^32.

### 7.4.2 Statistical error terms

The level of significance is set at  $\alpha = 5\%$ , aiming for a power of  $1 - \beta = 80\%$ .

### 7.4.3 Drop-outs

A drop-out rate of 15% was observed in an EEG neurofeedback trial with a follow-up 3 months after end of treatment. Based on these data and our own experience we assume a dropout rate of 20%. Although dropped-out from treatment, patients who discontinued treatment will be assessed at later assessment time points, if possible.

### 7.4.4 Sample size calculation

Based on a conservative effect size of 0.55 (compared to 0.65 quoted above), a t-test will have 80% power if 63 patients are analyzed (42 in the pooled intervention groups and 21 in the waiting control group), as determined using the software PASS 11. The width of the confidence intervals for the difference in means between two groups can then be expected to be about 0.88 SD for the pooled variance. The covariates incorporated into the analysis methods mean that the true power can be expected to be somewhat higher than that of the t-test reported here.

Taking into account a drop-out rate of about 20%, a total of 78 patients (26 per group) will be randomized.

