## 2 STUDY OBJECTIVES

### 2.1 Primary outcome

The number of objective binge-eating episodes (OBEs) over the past 14 days at post-treatment (t1), derived from the well-established Eating Disorder Examination, **will be compared between groups, correcting for the baseline value.** OBEs are consistently reported as the primary outcome measure in BED treatment trials. It will be determined whether neurofeedback results in a significantly lower number of OBEs over the past 14 days at post-treatment (t1) compared to the delayed control intervention and how fNIRS, EEG, and delayed control intervention compare.

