### 3.5 Premature termination of the trial

#### 3.5.1 Termination of the trial

The responsible investigator has the right to discontinue the trial

- if information emerges that affects the benefit/risk ratio of the trial;
- if actual recruitment and follow-up rates do not guarantee the necessary statistical power;
- if there are repeated serious adverse events (SAE) presumably associated with the trial.

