### 7.5.2 Planned methods for analysis

Primary analysis: The primary endpoint, the number of OBEs at post-treatment (t1) ~~and pre-treatment (t0)~~, will be investigated using ANCOVA with OBEs at t1 as the dependent variable, OBEs at t0 as a covariate as well as the stratification criteria. A closed-testing procedure will be used, meaning that the initial comparison will be between the two intervention groups combined and the waiting group and the three pair-wise tests (~~fNIRS vs. waiting group, EEG vs. waiting group and fNIRS vs. EEG~~) will be performed without adjustment if the global test is significant. The analysis will follow the intent-to-treat principle and will be based on the full analysis set. Every attempt will be made to acquire missing data. If data missing for the primary outcome can be expected to bias results in a meaningful way, multiple imputation will be performed. Further, the analysis of the primary outcome will be performed in the per-protocol set to evaluate the treatment effect for patients with good protocol adherence.

Secondary analyses: Recruitment and attrition rates will be described quantitatively and a qualitative analysis of the hurdles involved in recruitment and in maintaining patient commitment will be presented. Further secondary outcomes will be analyzed in an exploratory, descriptive manner, and will be evaluated presented with 95% CIs, as well as parametric or non-parametric tests, depending on the scale level and type of distribution of the observed variables. Multiple comparisons given three arms will be taken into account using e.g. Dunnett's test or Tukey's Honest Significant Differences and where all pair-wise comparisons will be made, independent of the result of a global test. Maintenance of treatment success over time will be evaluated. Predictors of treatment outcome will be identified using regression analyses.

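### Protocol 7.4.4 states 80% power at d = 0.55 with 42 vs 21 analysed; the t-test has 53% two-sided or 65% one-sided, and 0.88 SD is not the 95% interval width

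*Protocol*

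**What the plan says.** Protocol 7.4.2 sets alpha at 5% and aims for 80% power. Neither it nor any other section says whether the test is one- or two-sided. The wording of the hypothesis is directional: Protocol 2.1 says "It will be determined whether neurofeedback results in a significantly lower number of OBEs over the past 14 days at post-treatment (t1") than in the delayed-treatment group.

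Protocol 7.4.4 begins "Based on a conservative effect size of 0.55 (compared to 0.65 quoted above") and states that "a t-test will have 80% power if 63 patients are analyzed (42 in the pooled intervention groups and 21 in the waiting control group"), citing PASS 11. It adds: "The width of the confidence intervals for the difference in means between two groups can then be expected to be about 0.88 SD". It then says that the covariates should lift the true power somewhat above the t-test figure, so the 80% is the power before any covariate gain. Allowing for about 20% drop-out, 78 patients (26 per arm) are to be randomised.

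Protocol 7.5.2 explains why the groups are 42 and 21: "the initial comparison will be between the two intervention groups combined and the waiting group". Only if that test is significant do the three pairwise tests on the primary endpoint follow, without adjustment. SAP 4.1 repeats this. The SAP contains no sample-size section; item 1b of its CRED-nf checklist refers the reader back to the protocol.

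**The concern.** A two-sample comparison with 21 patients in the smaller group is a small one for an effect of 0.55 SD, so 80% power looked too high. The interval width looked too narrow for the same groups.

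At stake is the credibility of the formal test of the primary endpoint. If the planned effect is real, the stated design would miss it one time in five. At the recomputed power, the first test misses it about 47% of the time two-sided (1 − 0.526) or 35% one-sided (1 − 0.652). In those cases the fNIRS vs waiting-list, EEG vs waiting-list and fNIRS vs EEG contrasts on binge-eating episodes would be estimated but not tested. A reader who relies on 7.4.4 would also expect narrower intervals than the trial can give.

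**Working it through.** **Inputs.** d = 0.55, t-test, n₁ = 42, n₂ = 21 (Protocol 7.4.4); alpha = 5% (7.4.2); N = 78 randomised, so 52 vs 26 if all are analysed. Sidedness is not given, so both are computed. The calculation is in SD units, so the SAP's change from a 14-day to a 28-day count does not alter it at a given d.

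**1. Attempt to reproduce the 80%.**
- SE = √(1/42 + 1/21) = 0.2673 SD; df = 61.
- Noncentrality = 0.55 / 0.2673 = 2.058.
- Noncentral-t power: **52.6% two-sided, 65.2% one-sided**. The normal approximation gives 53.9% and 66.0%.

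Other readings within the planned design:

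| Analysed | d | Two-sided | One-sided |
|---|---|---|---|
| 42 vs 21 | 0.55 | 52.6% | 65.2% |
| 42 vs 21 | 0.65 | 66.8% | 77.6% |
| 52 vs 26 | 0.55 | 61.8% | 73.4% |
| 21 vs 21 | 0.55 | 41.3% | 54.3% |

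None gives 80%.

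**2. What would give 80%.** At 42 vs 21, solving for d gives 0.76 two-sided and 0.67 one-sided. At d = 0.55 with 2:1 pooling, 80 vs 40 (120 analysed) gives 80.4% two-sided, and 64 vs 32 (96 analysed) gives 81.0% one-sided. These sizes show how large the gap is; they are not a proposal.

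**3. Drop-out step.** 63 / 0.8 = 78.75 and 78 × 0.8 = 62.4. This is consistent with 78 and is not the source of the problem.

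**4. Interval width** = 2 × quantile × SE.
- 42 vs 21, 95%: 2 × 2.000 × 0.2673 = **1.07 SD**.
- 21 vs 21, 95%: 2 × 2.021 × √(2/21) = 2 × 2.021 × 0.3086 = **1.25 SD**.
- 42 vs 21, 90%: 0.89 with the t quantile, 0.88 with the normal quantile.
- Equal groups, 95%: 0.88 at 41 per group, 0.87 at 42 per group.

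**5. Covariate gain.** Adjusting for a baseline value correlated r with the outcome changes the effective effect to about 0.55 / √(1 − r²). The documents give no r, so 0.3 to 0.6 is an assumed range.

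| r | 42 vs 21, two-sided | 42 vs 21, one-sided | 52 vs 26, two-sided | 52 vs 26, one-sided |
|---|---|---|---|---|
| 0.3 | 56% | 69% | 66% | 77% |
| 0.5 | 65% | 76% | 74% | 84% |
| 0.6 | 72% | 82% | 81% | 88% |

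With 63 analysed, 80% needs r of about 0.69 two-sided or 0.57 one-sided.

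**The case against.** The strongest reply is that the analysis is not a plain t-test on 63 patients. It is an ANCOVA, the hypothesis is directional, the full analysis set is close to all randomised patients, and missing outcomes are multiply imputed (SAP 3.1 and 4.1). On favourable settings the planned analysis can reach 80%: one-sided with r of about 0.57, or two-sided with all 78 and r = 0.6. This stands as a reason to report a range. It does not rescue the stated figure, which 7.4.4 assigns to the t-test on 63 patients before covariates. Imputation also does not restore all the lost information, so the 52 vs 26 figures are an upper bound. It is fair, too, that the trial is labelled a feasibility study; but efficacy is its stated primary objective, and the 80% claim is the protocol's own.

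Several stronger readings are tempting, and the documents do not support them.
- **That 0.88 SD is a 90% interval.** It fits the 90% normal-quantile width, but 7.4.4 names no level. A one-sided equal-group calculation fits about as well: 42 per group gives 80.4% power and a 95% width of 0.87 SD. The source cannot be established.
- **That the pooled test controls every formal comparison.** It controls only the three pairwise tests on the primary endpoint. Protocol 7.5.2 and SAP 4.2.2 make the secondary comparisons without it, and SAP 4.1 still reports primary estimates and intervals if it fails.
- **That 0.55 is not conservative because of the 0.40 in 7.4.1.** The text reads "Preliminary data for BED showed an effect size within a treatment group of 0.40". A within-group effect is not comparable with a between-group d, and 7.4.4 calls 0.55 conservative only relative to 0.65.
- **That the stopping right rests on this figure.** Protocol 3.5.1 says "if actual recruitment and follow-up rates do not guarantee the necessary statistical power". It names no power value and is discretionary.
- **That a null result will be taken as no effect.** Neither document says so.

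**Conclusion.** Wrong as written. The 80% overstates the t-test's power by 27 percentage points two-sided (80 − 53) or 15 one-sided (80 − 65). The width of "about 0.88 SD for the pooled variance" understates the 95% width by 0.19 SD for pooled vs waiting list (1.07 − 0.88) and by 0.37 SD for a pair of arms (1.25 − 0.88).

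The power conclusion needs only inputs printed in the protocol and holds on either sidedness. The width conclusion assumes that 95% is the intended level, as it is for the secondary analyses in 7.5.2. The covariate range further assumes r between 0.3 and 0.6, a single baseline covariate, and the usual normal-theory approximation for an episode count; the small loss of degrees of freedom is ignored. Nothing here shows that the trial's tests or estimates are invalid. The error lies in the justification of the sample size.

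**What to change.** Keep N = 78 and restate Protocol 7.4.4 as follows:
- Name the sidedness and the confidence level.
- With 42 vs 21 analysed and d = 0.55, give power of 53% two-sided (65% if one-sided), and a detectable effect at 80% power of 0.76 SD (0.67 SD).
- Give expected 95% interval widths of 1.07 SD for pooled vs waiting list and 1.25 SD for each pair of arms.
- Replace the unquantified covariate gain with a range for assumed baseline–outcome correlations of 0.3 to 0.6. Two-sided, this is about 56–72% with 63 analysed and 66–81% as an upper bound with all 78. Add that 80% with 63 analysed needs r of about 0.69 two-sided or 0.57 one-sided.

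Item 1b of the SAP's checklist would then point to corrected figures. No patients, visits, tests or analysis sets change. The cost is a wording amendment and a less favourable stated power.
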